## **6.4 Treatment compliance**

For all study participants, study medication will be administered at the study unit.

Drug accountability must be recorded on the Drug Accountability form.

## **6.5 Concomitant medication(s)/treatment(s)**

### **6.5.1 Permitted concomitant treatments (medications and therapies)**

The following concomitant medications are permitted during the study:

- Paracetamol/acetaminophen for the treatment of mild symptoms (eg, headache or other pain), given at most every 6 hours to 8 hours, not exceeding 2g per day, and with a total of no more than 5g over 7 days.
- Ibuprofen, not exceeding 1.2g per day.
- Nasal corticosteroids for seasonal rhinitis and topical corticosteroids for controlled dermatological conditions.
- Oral contraceptives not exceeding 30µg ethinyl estradiol or postmenopausal hormonal replacement therapy (HRT) or implants, patches, or IUDs/IUSs delivering progesterone (for female study participants).

For all study participants: if a concomitant medication is required during the Washout Period and if there is no impact on the study participant's safety and the impact on quality of further study data is deemed to be minimal, the study participant can remain in the study after Sponsor approval. If the concomitant medication use does not violate these criteria and no drug allergy has been reported, the study participant will be permitted to continue in the study.

#### **6.5.1.1 Permitted Coronavirus Disease-2019 vaccination**

During the study, COVID-19 vaccinations are allowed as long as they are not administered in the 10 days prior to or in the 7 days after administration of the final dose of the study medication.

### **6.5.2 Prohibited concomitant treatments (medications and therapies)**

The following concomitant medications are prohibited during the study:

- Medicines known to strongly interact with CYP3A4 (both inducers [including St. John's Wort] and inhibitors).
- Medicines known to strongly affect gastric pH (excluding esomeprazole as used per protocol in Part A).

### **6.5.3      Rescue medication**

No rescue medication will be provided as part of this study.

### **6.6      Dose modification**

There is no dose modification allowed in UP0073.

### **6.7      Criteria for study hold or dosing stoppage (Part A and Part B)**

Study medication will be stopped if the study participant develops a medical condition (or laboratory abnormality or ECG change) that, in the opinion of the Investigator, compromises the study participant's ability to participate or compromises the study participant's safety.

In all cases, the study participant should be followed until the condition has resolved as agreed by the Investigator and the UCB Study Physician.

See the Schedule of Activities (Section 1.3) for data to be collected at the time of treatment discontinuation and follow up and for any further evaluations that need to be completed.

Detailed procedures for reporting SAEs and other safety events which may meet study hold criteria are provided in Appendix 8 (Section 10.8).

### **6.8      Treatment after the end of the study**

There are no plans for study participant continued care after the end of the study, since study participants are healthy volunteers.

[figure not shown]
## **7            DISCONTINUATION OF STUDY MEDICATION AND STUDY PARTICIPANT DISCONTINUATION/WITHDRAWAL**

### **7.1      Discontinuation of study medication**

#### **7.1.1      Liver chemistry stopping criteria**

Discontinuation of study medication for abnormal liver function should be considered by the Investigator when a participant meets one of the conditions outlined in [Figure 7-1](#) or if the Investigator believes that it is in best interest of the participant. Study medication will be discontinued immediately and permanently for a healthy participant if liver chemistry stopping criteria are met.

**Figure 7-1: Phase I Liver Chemistry Stopping Algorithm**

ALT=alanine transaminase; ULN=upper limit of normal

Specific assessments and follow up actions for potential drug-induced liver injury (PDILI) are provided in Appendix 6 (Section 10.6).

### 7.1.2 QTc stopping criteria

A study participant who meets either bulleted criterion based on a single 12-lead ECG reading will be withdrawn from study treatment. If there are abnormalities that are considered clinically significant for a particular study participant, ECG recordings will be performed in triplicate at 2- to 3-minute intervals (3 ECGs within a 5-minute timeframe) prior to the exclusion of the participant.

- QT corrected for heart rate using Fridericia's formula (QTcF)  $>500\text{ms}$  OR Uncorrected QT  $>600\text{ms}$
- Change from Baseline of QTcF  $>60\text{ms}$

For study participants with underlying bundle branch block, follow the discontinuation criteria listed below:

Baseline QTc with bundle branch block	Discontinuation QTc threshold with bundle branch block
<450ms	$>500\text{ms}$
450 to 480ms	$\geq 530\text{ms}$

If a clinically significant finding is identified (including, but not limited to, changes from Baseline in QTcF after enrollment), the Investigator or qualified designee will determine if the study participant can continue the study medication and if any change in study participant management is needed. This review of the ECG printed at the time of collection must be documented. Any new clinically relevant finding should be reported as an AE.

See the Schedule of Activities (Section 1.3) for data to be collected at the time of treatment discontinuation and follow up and for any further evaluations that need to be completed.

### 7.1.3 Renal toxicity stopping criteria

Participants must be discontinued from the study medication if renal toxicity considered possibly related to the study treatment occurs.

Laboratory tests suggestive of renal toxicity which should trigger further assessment may include:

- Increase in serum creatinine  $\geq 0.3\text{mg/dL}$  from Baseline **OR**
- Increase in serum creatinine to  $\geq 1.5$  times from Baseline **OR**
- New persistent albuminuria or clinically significant increase in preexisting albuminuria.

Any clinically significant findings in laboratory results for renal function will be monitored until resolution or stabilization.

### 7.1.4 Hypersensitivity reaction stopping criteria

Study participants will be informed that if they develop any symptoms suggestive of an hypersensitivity reaction (eg, rash, angioedema, or anaphylaxis), they should contact the Investigator immediately. The Investigator should assess the presenting symptoms to determine if this is possibly a hypersensitivity reaction.

If the event is not considered to be a hypersensitivity reaction, the Investigator should document this and the participant may continue dosing. If the event is possibly a hypersensitivity reaction, the Investigator will withhold dosing and arrange additional investigations. Study participants may be referred to a dermatologist for additional investigation. The event should be reported to UCB as an AESI.

- Two or more study participants have an hypersensitivity reaction that, based on reasonable medical judgement, could lead to significant toxicities that would be unacceptable for this study population **OR**
- Two or more study participants have a study medication-related severe hypersensitivity reaction (Grade 3 according to the Common Terminology Criteria for Adverse Events [CTCAE] classification) **OR**
- One or more study participants have a study medication-related hypersensitivity reaction of Grade 4 or 5 according to the CTCAE classification.

If any of the above events occur during the study, the following should take place:

- Further administration of the study medication will be suspended for all study participants.
- The SMC will meet as soon as possible and will provide recommendations regarding individual study participants, individual groups, the study overall, the suspension or continuation of dosing, the stopping or continuation of the study or the modification of the protocol.

Detailed procedures for reporting SAEs and other safety events which may meet study hold criteria are provided in Appendix 8 (Section 10.7).

### **7.1.5 General stopping criteria for the study - Part B only**

UCB will halt further dosing if any of the following criteria are met during the course of the study and following case review to confirm causality and seriousness and/or severity of reported events.

During the study, planned dosing and procedures must be discontinued or suspended for all remaining study participants who are yet to be dosed in the study and appropriate follow-up procedures established for (but not limited to) any of the following reasons: One study participant has an SAE considered related to the study medication as judged by the Investigator. Two or more study participants in a single cohort have a severe AE, similar clinically significant abnormal laboratory results or other clinically significant safety findings that would be unacceptable for this study population. If one of the stopping criteria for dosing and single dose escalation has been met, the SMC will meet as soon as possible to make a recommendation on discontinuation, pausing, or suspension of study medication dosing or on the stopping or continuation of the study. Consideration will be given to severity and relatedness of events. Further details on the role and process of ensuring close safety monitoring through the SMC are provided in the respective charters. See the Schedule of Activities (Section 1.3) for data to be collected at the time of treatment discontinuation and follow up. Temporary discontinuation

The Investigator or SMC may consider temporary discontinuation of dosing of study participants on a case-by-case basis (for Part B only).

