## **2.3        Benefit/risk assessment**

This study will not provide any benefit to the study population, ie, healthy study participants, instead it will provide relevant pharmacological and clinical safety information to support UCB0599 new formulation development as well as to support the further development of UCB0599 in Japanese and Chinese populations. In Phase 1 development of UCB0599, 5 studies (UP0030, TM0017, UP0023, UP0077, and UP0078) demonstrated that UCB0599 has acceptable safety, PK, and tolerability profiles for further clinical development.

Drug hypersensitivity is an important identified risk for UCB0599. Cardiac effects are an important potential risk based on nonclinical data. Overall, the majority of treatment-emergent adverse events (TEAEs) seen in the Phase 1 and Phase 2 studies were mild or moderate in intensity and resolved. In UP0030, 2 events of hypersensitivity were reported. An additional 2 events of hypersensitivity occurred in study participants who received UCB0599 in UP0077. A causal relationship between the reported events of drug hypersensitivity and UCB0599 is considered plausible. There have been no reports of anaphylaxis in the UCB0599 clinical program.

Based on the results of UP0030, drug hypersensitivity and symptoms commonly associated with anaphylaxis and angioedema have been considered adverse events of special interest (AESI) and an important identified risk, based on reasonable clinical judgment. To minimize the risks for study participants, the study team at UCB and the contract research organization (CRO) will continue to systematically review safety data and UCB0599 exposure data. The site will be informed and trained appropriately about the risk of a hypersensitivity reaction (such as rash, angioedema, or anaphylaxis) and the actions that need to be taken in case of a hypersensitivity reaction. The participant will be informed by the Investigator during the consent procedure about the risk of a hypersensitivity reaction and other important potential risks for UCB0599. Risk

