### **8.3.6.2 Renal function safety monitoring and management**

If a participant develops clinically significant renal dysfunction, repeat laboratory testing should be undertaken as soon as possible and other appropriate investigations may be arranged. An increase in serum creatinine of >25% from the previous value will trigger repeat testing within 48 hours. The Medical Monitor should be notified, and consideration should be given to more frequent monitoring.

Clinically significant renal dysfunction will trigger an SMC review.

Participants must be discontinued from study medication (but not necessarily from the study) if laboratory tests suggest evidence of renal toxicity (see Section 7.1.3 for renal toxicity stopping criteria and Section 7.2 for participant discontinuation/withdrawal from the study). Any clinically significant findings in laboratory results for renal function will be monitored until resolution or stabilization.

The SMC charter will include further details regarding the assessment of renal function.

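### Apart from the hypersensitivity rule in 7.1.4, Part A has no pre-set study-level hold; the pause after one related SAE is written for Part B only

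*Protocol*

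**What the plan says.** Protocol 7.1.5 is headed "General stopping criteria for the study - Part B only". Its first criterion is "One study participant has an SAE considered related to the study medication as judged by the Investigator". If it is met, dosing is discontinued or suspended for everyone still to be dosed, and the SMC meets to make a recommendation. The halt is not automatic: it comes "following case review to confirm causality and seriousness and/or severity of reported events". The second criterion begins "Two or more study participants in a single cohort have a severe AE, similar clinically significant abnormal laboratory results". The same section's provision on temporary discontinuation, and 7.1.6 on rechallenge, are also limited to Part B.

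Protocol 7.1.4 names no part, so it covers Part A. It suspends dosing for all participants, but only for hypersensitivity. Two of its three criteria need at least two participants. The third needs one: "One or more study participants have a study medication-related hypersensitivity reaction of Grade 4 or 5 according to the CTCAE classification".

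Protocol 6.7 is headed as criteria for a study hold or a dosing stoppage in both parts. Its criterion is individual: "Study medication will be stopped if the study participant develops a medical condition" that, in the investigator's opinion, compromises that person's participation or safety.

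Protocol 10.1.10 says that criteria for study holds due to AEs are in Section 8.3 and Appendix 3.

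On oversight, 4.1.2 and 9.8 provide for SMC review throughout the study, and 10.1.6 allows ad hoc SMC meetings when the sponsor thinks them appropriate. The only SMC review given a fixed time is after Cohort 3 in Part B (Protocol 9.8, SAP 5.8).

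**The concern.** The sponsor's own standard in Part B is that one related SAE is enough to stop and look before anyone else is dosed. Part A is expressly outside that standard, although it gives up to 42 people six 180mg doses each and includes two formulations that the protocol calls new.

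The risks at issue are ones the protocol itself names. Section 2.3 calls drug hypersensitivity an important identified risk, with four earlier events across two studies and a plausible causal link. It adds: "Cardiac effects are an important potential risk based on nonclinical data". Section 7.1.4 deals with the first risk in part. No study-level rule deals with the second in Part A. ECGs on Part A dosing days are scheduled on Day 1 only (Table 1-3), so ECG monitoring does not stand in for a rule.

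At stake is whether the other participants keep being dosed while the first related SAE is assessed. Without a pre-set rule, that is decided case by case, after the event is known, by people with an interest in keeping a fixed dosing calendar.

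**Working it through.** No figure in the plan has to be reproduced. The check is a reading of every section that could hold a Part A rule.

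| Section | Covers Part A? | Trigger | Effect |
|---|---|---|---|
| 6.7 | Yes | Condition, laboratory or ECG change in one person | Stops that person |
| 7.1.1 to 7.1.3 (liver, QTc, renal) | Yes | Individual thresholds | Stops that person |
| 7.1.4 | Yes | Hypersensitivity only | Suspends dosing for all; SMC meets |
| 7.1.5 | No | One related SAE, or two participants in a cohort | Halts those not yet dosed, after case review |
| 8, opening text | Yes | Immediate safety concern | Sponsor discussion about the affected person |
| 8.3.6.2 | Yes | Renal: "Clinically significant renal dysfunction will trigger an SMC review" | Review, not a hold |
| 8.4 | Yes | Periodic signal review | No threshold |
| 4.1.2, 9.8, 10.1.6 | Yes | Ongoing or ad hoc SMC review | Discretionary |
| 10.1.10 | Yes | Sponsor may terminate | Discretionary |
| 8.3 and Appendix 3 (cited by 10.1.10) | Yes | Definitions, recording, reporting, follow-up | No hold threshold |

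Applied to specific events:

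| Event | Pre-set hold in Part A? | Pre-set hold in Part B? |
|---|---|---|
| One related Grade 4 or 5 hypersensitivity reaction | Yes (7.1.4) | Yes |
| Two related Grade 3 hypersensitivity reactions | Yes (7.1.4) | Yes |
| One related serious hypersensitivity reaction below Grade 4 | No | Yes, after case review (7.1.5) |
| One related cardiac SAE | No | Yes, after case review (7.1.5) |
| Two related cardiac SAEs | No | Yes, after case review (7.1.5) |

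Scope, from the planned numbers (replacements in Part B ignored):

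- Part A: 42 participants × 6 doses = 252 active doses.
- Part B: 2 ethnic groups × (4 + 4 + 4) = 24 participants on active drug; × 2 doses = 48.
- Share of actively dosed participants: 42 / (42 + 24) = 42/66 = 64%.
- Share of active doses: 252 / (252 + 48) = 252/300 = 84%.

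Doses still planned for the other 41 participants after the Period k dose, if all 42 are dosed in step: 41 × (6 − k) = 205, 164, 123, 82, 41 and 0 for k = 1 to 6. The enrolment schedule is not given; with staggered entry the range is 0 to 41 × 6 = 246. These counts apply to a related SAE that does not trigger 7.1.4.

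How often a one-SAE rule would be used depends on a rate the documents do not give. For an assumed per-participant probability p of a related SAE, the chance of at least one among 42 is 1 − (1 − p)^42: 19.0% at p = 0.5%, 34.4% at 1%, 57.2% at 2% and 88.4% at 5%. The values of p are assumptions and say nothing about the true risk.

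**The case against.** The restriction to Part B looks deliberate. Section 7.1.5 speaks of dose escalation, and Part B is double-blind, goes to 360mg in successive cohorts and enrols the groups being bridged. Part A is open-label at a fixed 180mg, within the single-dose range already studied, with participants confined to the clinic. SAEs and AESIs are reported within 24 hours, the SMC reviews data throughout, ad hoc meetings are possible, and the sponsor can stop the study at any time. The Part B rule itself waits for case review. The documents cite no requirement that a fixed-dose bioavailability part carry such a rule.

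Much of this stands. A reader might infer that Part A has no study-level stopping rule at all, or is unsupervised. Neither is supported: 7.1.4 suspends all dosing after one related Grade 4 or 5 hypersensitivity reaction, and the discretionary routes do reach Part A. A reader might also take the 6.7 heading as proof that a hold was written and then lost. The heading offers a hold or a stoppage, and its text supplies a stoppage, so it proves no such thing.

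The fixed-dose argument is weaker than it looks. Part B's 360mg is also below the 450mg single dose already tested (4.3), and Part B includes the same 180mg dose; the sponsor still judged one related SAE enough to halt there. The discretionary routes allow a pause but do not commit anyone to one. Sections 9.8 and 10.1.6 refer to Section 4.1 for the SMC, where the only SMC text is under Part B.

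**Conclusion.** The point holds in limited form. Outside hypersensitivity, the protocol sets no study-level hold for Part A, and within hypersensitivity a single related reaction below Grade 4 meets none either. In those cases, whether the other participants are paused is left to judgement. It is a design choice worth changing: 7.1.5 expressly leaves Part A out, 10.1.10 sends the reader to hold criteria that are not in the cited places, and the remedy is the sponsor's own rule.

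The 84% of active doses shows how much dosing lies outside the single-related-SAE rule. It would be wrong to read it as a share of risk, since the documents give no event rate.

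The conclusion rests on the protocol and SAP text. The SMC charter was not available and might contain a Part A threshold, but the protocol points to none. The references to Appendix 8 in 6.7 and 7.1.4 (the latter with the section number of Appendix 7) lead to appendices marked not applicable. Those errors are editorial and carry no weight here.

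**What to change.** Add to 6.7 or 7.1.5: in Part A, one SAE judged related to study medication pauses, after case review, further dosing of all participants until the SMC makes a recommendation. State in 4.1.1 that the SMC covers Part A. Point 10.1.10 to 7.1.4 and 7.1.5, and to 6.7 if the new rule is placed there. As editorial corrections, 6.7 and 7.1.4 should cite Appendix 3 and 8.3.6 for reporting.

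Do not simply delete the Part B restriction from the heading. That would bring the two-participant criterion into Part A unadapted. Its wording does not require relatedness (which enters only through case review and the SMC's deliberation), and the cohorts the protocol numbers, 2 to 4, are all in Part B. If all 42 Part A participants were read as one cohort, two unrelated severe AEs weeks apart could meet it. If that criterion is extended, require related severe AEs and replace the single cohort with a defined Part A group.

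The cost is a few sentences, with no change to sample size or PK analysis. The real downside is operational. A pause could move the dosing days (1, 6, 11, 19, 24, 29) and lengthen confinement and the 20-day esomeprazole course. For a group dosed in step, a review finished before the next dosing day moves nothing; the gaps between doses are 5, 5, 8, 5 and 5 days. A longer pause could cost completers. Part A withdrawals are not replaced, and only 42 − 36 = 6 can be lost before the target is missed. On the plan's own assumptions (residual variance 0.0782, limits 0.8 to 1.25, true ratio 1.0, one-sided 5% tests, 2n − 4 degrees of freedom), power is 91.2% with 36 completers, 89.3% with 34 and 84.1% with 30.

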### **7.1.6 Rechallenge**

The Investigator after agreement with the SMC may consider rechallenge of study participants on a case-by-case basis (for Part B only).

## **7.2 Participant discontinuation/withdrawal from the study**

Participants are free to withdraw from the study at any time, without prejudice to their continued care.

A participant may withdraw from the study at any time at his/her own request, or may be withdrawn at any time at the discretion of the Investigator for safety, behavioral, compliance, or administrative reasons.

If the participant withdraws consent for disclosure of future information, the Sponsor may retain and continue to use any data collected before such a withdrawal of consent.

If a participant withdraws from the study, he/she may request destruction of any samples taken and not tested, and the Investigator must document this in the site study records.

See the Schedule of Activities (Section 1.3) for data to be collected at the time of study discontinuation and follow up and for any further evaluations that need to be completed.

Participants should be withdrawn from the study if any of the following events occur:

1. Participant develops a clinically relevant medical condition (physical or psychiatric) that, in the opinion of the Investigator, jeopardizes or compromises the study participant's ability to participate in the study or makes it unsafe to continue.
2. Participant is noncompliant with the study procedures or medications in the opinion of the Investigator.

3. Participant's laboratory tests suggest evidence of renal toxicity.
4. Participant takes prohibited concomitant medications as defined in this protocol.
5. Participant withdraws his/her consent.
6. There is confirmation of a pregnancy during the study, as evidenced by a positive serum pregnancy test.
7. Participant has an anaphylactic reaction after their first administration.
8. The Sponsor or a regulatory agency requests withdrawal of the participant.

Investigators should attempt to obtain information on study participants in the case of withdrawal.

Investigators should contact the UCB Medical Monitor, whenever possible, to discuss the withdrawal of a study participant in advance. See Appendix 1 (Section 10.1 for details on study discontinuation).

Participants who withdraw in Part A will not be replaced, and participants who withdraw in Part B will be replaced up to a maximum of 6 study participants.

